3.2. Endpoints

Primary Endpoint

The default primary endpoint is clinical status (8-point ordinal scale) on Study Day 8:

1. Not hospitalized, no new or increased limitations on activities;
2. Not hospitalized, but new or increased limitation on activities and/or requiring new or increased home oxygen, CPAP, or BiPAP;
3. Hospitalized, not requiring new or increased supplemental oxygen - no longer requires ongoing medical care;
4. Hospitalized, not requiring new or increased supplemental oxygen - requiring ongoing medical care (COVID-19 related or otherwise);
5. Hospitalized, requiring new or increased supplemental oxygen;
6. Hospitalized, requiring new or increased non-invasive ventilation or high-flow oxygen devices;
7. Hospitalized, on invasive mechanical ventilation or extracorporeal membrane oxygenation (ECMO);
8. Death.

Key Secondary Endpoints

One of the key secondary endpoints is time to sustained recovery (up to and including Study Day 60) and is defined as the first day on which the subject satisfies 1 of the following 3 categories from the clinical status ordinal scale (and does not return to a score of ≥ 4 up to and including Study Day 60):

1. Not hospitalized, no new or increased limitations on activities;
2. Not hospitalized, but new or increased limitation on activities and/or requiring new or increased home oxygen, CPAP, or BiPAP;
3. Hospitalized, not requiring new or increased supplemental oxygen - no longer requires ongoing medical care.

The other key secondary endpoint is whether the subject did not satisfy one of the following two categories from the ordinal scale up to and including Study Day 29. This analysis will only be completed for those subjects with baseline ordinal score of 5 or 6:

7. Hospitalized, on invasive mechanical ventilation or ECMO;
8. Death.

If the key secondary endpoints are different than what is covered in this master SAP, it will be highlighted for each individual investigational intervention in the corresponding stage-specific appendix.

Other Secondary Endpoints

The other secondary endpoints are:

Efficacy

- Time (days) from Study Day 1 to the first day for which a subject is assessed to be at least 1 category lower (improvement) than the subject's baseline ordinal score up to and including Study Day 60;
- Time (days) from Study Day 1 to the first day for which a subject is assessed to be at least 2 categories lower (improvement) than the subject's baseline ordinal score up to and including Study Day 60;

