In this approach, `timevariable` represents the time until the event in question (e.g., recovery), `censorvariable` represents the censoring variable (e.g., 0= event observed, 1= event did not occur at the time of withdrawal, discharge, lost-to-followup, etc), and `treatmentvariable` represents the intervention (e.g., 0= remdesivir + placebo, 1= remdesivir + new treatment).

To perform a Cox proportional hazards analysis and generate the treatment hazard ratio along with its Wald confidence interval and p-value from the score test after adjusting for other covariates, the following SAS pseudocode will be used.

```
proc phreg data=dataset;
  class treatmentvariable(ref=placebolabel) othercovariates;
  model timevariable * censorvariable(1) = treatmentvariable othercovariates /
  ties=efron;
  hazardratio treatmentvariable / diff=ref cl=wald;
```

```
ods output hazardratios = hrest globaltest=pvalue;
run;
```

To assess the assumption of proportional hazards for Cox models, Kaplan-Meier curves for each treatment arm will be produced (PH assumption supported if curves do not cross). Restricted mean survival time along with its 95% CI will be reported to assess whether the results change if the PH assumption is not satisfied.

Proportional Odds analysis without MI:

The following SAS pseudocode will be used to perform the proportional odds analysis with treatment, baseline ordinal score and baseline steroid use as covariates to generate the treatment odds ratio, p-value, and predicted probabilities of the ordinal scale levels by treatment and ordinal score using complete data

```
proc logistic data=dataset out=imp_parms plots(only)=effect(x= ordscore_d8
  sliceby =baseordscorevar*trtvar individual connect);
  class baseordscorevar (param=ref ref=5) basesteroidusevar (param=ref ref=no
steroid use) trtvar (param=ref ref=placebolabel);
  model ordscore_d8 = trtvar baseordscorevar basesteroidusevar;
  oddsratio trtvar;
  ods output oddsratioswald = orest;
run;
```

For the endpoints analyzed by proportional odds, odds ratios between the binary progression strata will be computed, to support data understanding. For example, odds ratio, confidence intervals from logistic regression will be reported for treatment effect for the binary endpoint of OS= 1-7 vs 8, then OS= 1-6 vs 7-8, etc. Similar odds ratios across these 7 2x2 tables will support the proportional odds assumption.

95% Blaker confidence intervals for proportions/percentages:

```
proc freq;

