	Primary with Sensitivity Imputation 1	
 Use similar imputation methods for intermittent missingness and missing data after death. Multiple Imputation will be used for all subjects missing data after last assessment regardless of their discharge status at the last assessment.
	Primary with Sensitivity Imputation 2	
Use complete data defined as follow:
 
 If a subject is discharged from the hospital to another location other than LTAC, hospice care or other hospital, has intermittent missing ordinal score and reported an ordinal score of 1 or 2 after the missing score then: 
 Impute the intermittent missing ordinal score as 1 if the scores reported before and after the missing value are both 1 and no change in oxygen use or hospitalization status after discharge to a location other than hospice, long term acute care or other hospital. Impute the intermittent missing ordinal score as 2 after discharge to a location other than hospice, long term acute care or other hospital if the subject doesn't fall into the category above and subject is not hospitalized at the time point. LOCF will be used for remaining intermittent missingness of ordinal scores for the next planned assessment. All missing scores after death will be assigned an ordinal score of 8 Subjects discharged from the hospital to a location other than LTAC, hospice care or other hospital at their last assessment will be assigned a score of 2 for all timepoints after last assessment. Impute all remaining missing data after last assessment using last observation carried forward.
	Sensitivity	
 Same imputation as the primary analysis
	Supplemental	
 Same imputation as the primary analysis
	Subgroup	
 Repeat analysis for each subgroup using same imputation as primary analysis for this endpoint.
Key Secondary Endpoints		
1. Time to Sustained Recovery	Primary	
 Use the complete data for ordinal score to derive sustained recovery. Subjects whose last assessment in the study is prior to Day 57 (beginning of Day 60 window) will be considered not recovered and censored at the date of their last assessment. Death prior to recovery will be considered not recovered and censored at expected study Day 60.

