8.2. Secondary Efficacy Analyses

8.2.1. Key Secondary Efficacy Analyses

Recovery will be defined as having a value of 1, 2, or 3 on the clinical status 8-point ordinal scale. The time to sustained recovery will be defined as the elapsed time (in days) from Study Day 1 to the day prior to the earliest recorded day at which a subject reaches recovery or hospital discharge and doesn't worsen (ordinal score > 3) up to and including Study Day 60. For example, a hospitalized subject with an ordinal score of 3 on Study Day 7 and doesn't worsen up to and including Day 60 will have a time to sustained recovery of 6 days, since ordinal score is reflective of the prior 24-hours.

For the primary analysis of sustained recovery endpoint, any subjects whose last assessment in the study is prior to an observed recovery will be censored at the day of their last observed assessment. For the sensitivity analysis of this endpoint, subjects whose last assessment in the study is prior to an observed recovery before Day 57 (beginning of Day 60 window) and who were discharged to a location other than LTAC, hospice care, or other hospital will be considered recovered and censored at Day 60. For both primary and sensitivity analysis of this endpoint, subjects who complete follow-up but do not experience sustained recovery will be censored at the day of their Study Day 60. All deaths that occur on or before Study Visit Day 60 will be considered not recovered and censored at Day 60. Note that we do not expect many subjects to worsen after discharge.

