If a subject's last assessment is before Day 57 and is discharged to a location other than hospice, another hospital, or long-term care facilities, the subject will be considered recovered at the time of discharge for the sensitivity analysis but may be reviewed by the Endpoint Review Committee, if other data suggests the subject may not be recovered (e.g., to a location other than a private residence or discharged on high flow oxygen). If a subject is discharged to hospice or another hospital, or is a special case where recovery handling may be unclear, the subject's data may be reviewed by the Endpoint Review Committee to make the determination of whether the subject should be considered to have sustained recovery and, if so, at what time point in the analyses. Subject data to be reviewed as part of this determination will include the reported clinical status scores while hospitalized, where the subject was discharged to (e.g., private residence, rehabilitation facility, long-term care/nursing home, comfort care), and any information regarding readmittance. Additional information may be solicited to assess recovery.

Refer to [Table 6](#) for a list of covariates and subgroup analyses for this endpoint. Refer to [Table 7](#) for imputation methods to be applied to this endpoint.

The main analysis of the first key secondary endpoint (time to sustained recovery up to and including Study Day 60) conducts a score test to compare treatment to control up to and including Study Day 60. The treatment median survival time, confidence intervals and p-value from the score test will be presented ([Table 28](#)). Restricted mean recovery time estimates will be provided for each treatment group and actual baseline ordinal score stratum as well as the difference in restricted mean recovery time between treatment groups within each of the baseline ordinal score strata ([Table 29](#)).

Kaplan-Meier curves for each treatment arm will be presented and supplemented with the hazard ratio estimate, p-value, and the number of subjects at risk in each treatment at Study Day (not necessarily actual Study Days 1, 3, 5, 8, 11, 15, 22, 29, and 60) ([Figure 8](#)).

If the key secondary endpoint is different than what is covered in this SAP, it will be highlighted for each individual stage in the corresponding stage-specific appendix along with the subsequent analysis.

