	Treatment A (N=X)	6	x	x	x.x	x.x, x.x	x.x, x.x	x.xx	x.xx, x.xx	x.xx, x.xx
	Treatment B (N=X)		x	x	x.x	x.x, x.x	x.x, x.x			
	Treatment A (N=X)	7	x	x	x.x	x.x, x.x	x.x, x.x	x.xx	x.xx, x.xx	x.xx, x.xx
	Treatment B (N=X)		x	x	x.x	x.x, x.x	x.x, x.x			
	Treatment A (N=X)	Any BOS	x	x	x.x	x.x, x.x	x.x, x.x	x.xx	x.xx, x.xx	x.xx, x.xx
	Treatment B (N=X)		x	x	x.x	x.x, x.x	x.x, x.x			

N = Number of subjects in the specified treatment group, actual baseline ordinal score, and analysis population.

n = Number of recovered subjects.

Difference is the difference in the restricted mean recovery time between active treatment to placebo.

^a Tau is the truncation time point for the Restricted Mean Survival Time analysis and is equal to the minimum of the largest observed times in each group.

Programming

Within an actual baseline ordinal score stratum:

```
proc lifetest data=enrevent plots=(rmst) method=breslow rmst(cl);
by stratum;
time evntday * Censor(1);
strata trtcode /diff=all;
ods output rmst=rmst;
run;
```

Table 30: Proportion of Subjects Alive and Without Respiratory Failure through Day 29 — mITT Population

Analysis/Subgroup	Category	Treatment A (N=x)		Treatment B (N=x)		Odds Ratio			Risk Difference ^g			P-value ^h
		n	% (95%CI) ^f	n	% (95%CI) ^f	Estimate	95% CI	80% CI	Estimate	95% CI	80% CI	
Initial model, Age, Baseline OS, Dexamethasone Use, and CRP ^a	-	x	x.x (x.x, x.x)	X	x.x (x.x, x.x)	x.x	x.x, x.x	x.x, x.x	x.x	x.x, x.x	x.x, x.x	0.xxx
Primary with Sensitivity Imputation 1 ^b	-	x	x.x (x.x, x.x)	X	x.x (x.x, x.x)	x.x	x.x, x.x	x.x, x.x	x.x	x.x, x.x	x.x, x.x	0.xxx
Sensitivity Analysis 1: Baseline OS and Steroid Use ^c	-	x	x.x (x.x, x.x)	x	x.x (x.x, x.x)	x.x	x.x, x.x	x.x, x.x	x.x	x.x, x.x	x.x, x.x	0.xxx
Supplemental Analysis 1: Impact of age and duration of symptoms prior to enrollment ^d	-	x	x.x (x.x, x.x)	x	x.x (x.x, x.x)	x.x	x.x, x.x	x.x, x.x	x.x	x.x, x.x	x.x, x.x	0.xxx
Subgroup Analyses^e												
Baseline Ordinal Score	5	x	x.x (x.x, x.x)	x	x.x (x.x, x.x)	x.x	x.x, x.x	x.x, x.x	x.x	x.x, x.x	x.x, x.x	0.xxx
	6 or 7	x	x.x (x.x, x.x)	x	x.x (x.x, x.x)	x.x	x.x, x.x	x.x, x.x	x.x	x.x, x.x	x.x, x.x	0.xxx
Repeat for all subgroups from Table 6		x	x.x (x.x, x.x)	x	x.x (x.x, x.x)	x.x	x.x, x.x	x.x, x.x	x.x	x.x, x.x	x.x, x.x	0.xxx

CI=Confidence Internals. OR=Odds Ratios. NA=Not applicable.

N=Number of subjects in the modified-intent-to-treat (mITT) population. n=Number of subjects without respiratory failure or death through Day 29.

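### Table 29 takes the restricted-mean horizon from the outcome data in each stratum, so in small or low-risk strata it can fall short of Day 60 and shrink the between-arm difference

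*SAP*

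**What the plan says.** SAP Section 6.1 gives the restricted mean its role: "Restricted mean survival time along with its 95% CI will be reported to assess whether the results change" if proportional hazards does not hold. Section 8.2.1 applies it to the first key secondary endpoint: "Restricted mean recovery time estimates will be provided for each treatment group and actual baseline ordinal score stratum", together with the between-arm difference in each stratum. Neither section fixes a horizon.

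The horizon appears only in the Table 29 shell (Appendix 1, Section 14.2). Footnote a makes tau "equal to the minimum of the largest observed times in each group". The programming note runs "Within an actual baseline ordinal score stratum" and calls "proc lifetest data=enrevent plots=(rmst) method=breslow rmst(cl", with no truncation time supplied. The shell has rows for baseline scores 5, 6, 7 and Any BOS, in both mITT and ITT, and a column that prints tau.

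Three censoring rules decide how large an arm's largest time can be:

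- Deaths (Table 7, Section 6.5.1): "Death prior to recovery will be considered not recovered and censored at expected study Day 60".
- Completers who never reach sustained recovery are censored at their Study Day 60 (Section 8.2.1).
- Subjects last assessed before Day 57 are censored at that assessment (Table 7).

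The endpoint and the Table 29 title both run through Day 60. Times are elapsed days. In the example in Section 8.2.1, a subject who first scores 3 on Day 7 "will have a time to sustained recovery of 6 days, since ordinal score is reflective of the prior 24-hours". On that scale Day 60 is 59 elapsed days.

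**The concern.** Under these rules, one death or one unrecovered completer is enough to put an arm's largest time at Day 60. A late recovery puts it close to Day 60. An arm with none of these has a shorter largest time, and that time becomes tau for both arms. This happens when everyone in the arm recovers early, or when its only non-recovered subjects are lost early.

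Where the short arm has fully recovered, it loses nothing by truncation, because its Kaplan-Meier curve is already at zero. Only the other arm's remaining unrecovered days are removed. The difference is pulled toward zero in the situation where one arm has done best, and one worse outcome in that arm can make its reported advantage larger. The quantity estimated then depends on the outcome, and it may differ between strata and between the mITT and ITT rows.

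**Working it through.** The plan gives no numerical tau or restricted mean, so there is no figure to reproduce. The inputs from the documents are the tau rule and censoring rules above, about 100 subjects per active arm (SAP Section 4.1), and the Day 8 control distribution (Table 4: 3.5% dead, 24.2% ventilated or on ECMO). Stratum sizes, Day 60 non-recovery and recovery-time distributions are assumptions.

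**1. How often an arm has nobody carried to Day 60.** With n subjects and non-recovery (including death) probability p, the chance is (1 − p)^n:

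| n per arm | p = 2% | 3.5% | 5% | 10% |
|---|---|---|---|---|
| 20 | 0.67 | 0.49 | 0.36 | 0.12 |
| 30 | 0.55 | 0.34 | 0.22 | 0.04 |
| 50 | 0.36 | 0.17 | 0.08 | 0.005 |
| 100 | 0.13 | 0.03 | 0.006 | 0.000 |

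For at least one of two arms, the chance is 1 − [1 − (1 − pA)^n][1 − (1 − pB)^n]. With n = 50 and pB = 8%, 0.92^50 = 0.015.

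- pA = 2%: 0.98^50 = 0.364, giving 1 − 0.636 × 0.985 = 0.37.
- pA = 3%: 0.97^50 = 0.218, giving 1 − 0.782 × 0.985 = 0.23.

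Late recoveries lower these chances somewhat; early losses are not modelled.

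**2. What truncation removes.** Take a constructed stratum of 30 against 30, in elapsed days.

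- Arm A: 6, 8, 6, 5, 3 and 2 recoveries on days 3, 5, 8, 11, 14 and 20. All recover.
- Arm B: 5, 6, 5, 4, 3 and 2 recoveries on the same days, one each on days 28 and 35, and 3 subjects censored at 59.

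Nobody is censored before 59, so the restricted mean is the average of min(time, tau).

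- Rule as written, tau = 20: A = 243/30 = 8.10; B = 311/30 = 10.37; difference −2.27 days.
- Fixed tau = 59: A = 243/30 = 8.10; B = 451/30 = 15.03; difference −6.93 days.
- Change one arm A subject from recovery on day 20 to death (carried to 59). Tau returns to 59, A = 282/30 = 9.40, and the difference is −5.63.

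Under the written rule, one death in arm A moves its reported advantage from 2.27 to 5.63 days. If that subject is instead lost on day 24, tau is 24.

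**3. Simulated size, 50 per arm.** Recovery times among recoverers were drawn from an assumed distribution, with a set proportion never recovering.

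- Lognormal times, medians 6 v 8 days, log-scale SD 0.8, non-recovery 2–3% v 8%: tau fell below elapsed day 55 in 20–32% of replicates. In those, the mean difference was about −4.1 days under the rule and −6.5 at day 59, a cut of 2.4/6.5 = 37%. Averaged over all replicates, the shift is about 0.20 × 2.4 = 0.5 to 0.32 × 2.4 = 0.8 days.
- Exponential times, means 6 v 8 days, non-recovery 2% v 8%: tau below 59 in 38%; −3.02 v −5.78 in those (a cut of 48%); −3.97 v −5.01 overall, a shift of 1.04 days.
- Exponential, 3.5% v 10%: 17%; −3.43 v −6.83 (a cut of 50%); −4.58 v −5.15 overall, a shift of 0.57 days.
- Exponential, 5% v 5%: 15%; −1.59 v −2.01 (a cut of 21%); overall shift 0.07 days.
- At 10% v 15% non-recovery the overall shift is near zero.

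**4. The Any BOS row.** With 100 per arm, Day 8 deaths alone at the Table 4 rate leave an arm with nobody carried to Day 60 with probability 0.965^100 = 0.028. At 5% total non-recovery it is 0.95^100 = 0.006. Later deaths and ventilated subjects who do not recover lower it further.

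**The case against.** The strongest reply is that the row that matters is hardly touched. The restricted mean is a check on the Cox result. That model pools the strata, so its counterpart is the Any BOS row, where tau will almost always be Day 60. This stands. A reader might infer that the proportional-hazards check as a whole is compromised; step 4 does not support that.

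Second, the simulated sizes rest on favourable recovery rates that the documents do not give. At 92% recovery in both arms of 50, the chance that either arm is complete is only 1 − (1 − 0.015)^2 = 3%. The halved differences also apply only to replicates where tau fell. Both points stand, so the day differences are illustrations and not expected effects.

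Third, both arms share one tau, so each contrast is valid at its own horizon, and Table 29 prints tau. A reader might infer that the rule manufactures benefit. It does not: when it bites, it attenuates the difference. Printing tau reveals the truncation but does not let a reader recover the Day 60 difference.

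Fourth, the rule is pre-specified, sits in a supporting table of a master SAP that a stage-specific appendix may supersede, and leaves the primary Day 8 analysis alone. All true. Being pre-specified does not make the horizon fixed, however, and the endpoint already has a natural one.

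**Conclusion.** The point holds as a minor improvement to a supporting analysis. It applies where an arm of a stratum has neither a subject carried to Day 60 nor a late recovery. That is plausible for baseline score 5 or any small stratum with few deaths, and negligible for Any BOS or where both arms have deaths or unrecovered completers. At 50 per arm with 2–3% v 8% non-recovery, expect it in roughly 20–30% of strata, with the difference cut by about a third to a half when it occurs and by about 0.5–0.8 days on average (about 1 day with exponential times at 2% v 8%). These figures depend on assumed stratum sizes, recovery rates and time distributions. The documents do not support any claim that the primary endpoint, the Cox analysis or the pooled restricted mean is materially affected. The stage-specific SAP appendix was not available and could already set another horizon.

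**What to change.** Replace footnote a with a pre-specified tau of Study Day 60, stated as 59 elapsed days on the Section 8.2.1 scale, for every stratum and both populations in Table 29. Pass that value to the program. Where an arm's last time is a recovery and everyone still at risk has recovered, hold its curve at zero to tau. Use a shorter horizon, stated in the table, only where an arm's last time is a censoring before Day 60; in those rows tau remains data-dependent, which cannot be avoided.

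The cost is one footnote and a small code change. The sponsor should first confirm how the chosen procedure handles a tau beyond an arm's largest observed time. The code specifies method=breslow, whose curve ends slightly above zero and not at it. In a simulation of the same kind, that estimator barely changed the comparison (−3.5 v −6.3 days, against −3.6 v −6.2 with Kaplan-Meier), but the handling should be settled before the code is fixed.
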